5.5. Concomitant and Post-study Treatment(s)

Apart from paracetamol/acetaminophen, hormone replacement therapy and systemic contraceptives no concomitant medication or therapy will be allowed.

The subjects should be instructed that no other medication is allowed, including herbal remedies, vitamin supplements and over-the-counter products, without the consent of the PI.

Medication, which is considered necessary for the subject's safety and well-being, may be given at the discretion of the PI during the residential period.

When any medication is required, it should be prescribed by the PI. Following consultation with AstraZeneca Lead Physician, the PI should determine whether or not the subject should continue in the study. Administration of concomitant medications that may influence the measurement of the PK endpoints may be documented as a protocol deviation after consultation of the PI with AstraZeneca Lead Physician.

5.6. Treatment Compliance

Dosing will take place at the Parexel Early Phase Clinical Unit.

The administration of all IMPs will be recorded in ClinBase™.

Compliance will be assured by direct supervision and witnessing of IMP administration. After IMP administration, a check of the subject's mouth and hands will be performed.

Drug Accountability, Dispensing and Destruction

The IMP provided for this clinical study will be used only as directed in the CSP.

In accordance with GCP, the investigational site will account for all supplies of IMP. Details of receipt, storage, assembly/dispensing and return will be recorded.

All unused supplies of the IMP will either be destroyed by Parexel or returned at the end of the study in accordance with instruction by the Sponsor.

5.7. Discontinuation of Investigational Product and Withdrawal from Study

Dosing for any individual subject must be stopped if the subject experiences a possibly IMP-related SAE or a possibly IMP-related significant non-serious AE, which in the opinion of the Principal Investigator warrants discontinuation of the subject from the active protocol for his or her well-being.

Subjects must be discontinued from IMP in the following situations:

- Healthy subject decision. The healthy subject is at any time free to discontinue treatment, without prejudice to further treatment.
- Severe non-compliance to study protocol.

- Any significant and clinically relevant changes in the safety variables (eg, ECG, BP, pulse, tympanic temperature, laboratory assessments and AEs) making the continuation of IMP administration unjustified.
- Any case of PHL according to [Appendix C](#).
- Study specific withdrawal criteria: If the subject reports symptoms which are considered unacceptable by the subject or the PI, he/she must be withdrawn from the study. In particular:
 - Any other severe or SAE that is judged as possibly related to verinurad by the Investigator.
 - Study treatment must be stopped if a subject has elevated serum creatinine levels greater than 1.5 times the pre-treatment value and retest of the creatinine should be performed as soon as possible (see [Appendix D](#)).
 - In subjects who report symptoms that indicate acute UA nephropathy including flank pain, nausea, or vomiting, treatment must be permanently discontinued. [Appendix D](#) contains guidelines on management of such subjects.
 - See [Appendix D](#) for details on the handling of renal-related or urolithiasis treatment-emergent AEs, and the handling of serum creatinine elevation, which includes criteria for stopping treatment.
 - Pregnancy.
 - Any confirmed COVID-19 case that warrants discontinuation in the judgment of the Investigator or Sponsor to protect the safety of the subject, other study participants or study site staff.

The appropriate AE form in the CRF must be completed.

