3. STUDY DESIGN

3.1. Overall Study Design and Flow Chart

This study will be a single-centre, randomised, open-label, single-dose, 5-period, 5-treatment, crossover study in healthy male and female subjects.

The study will comprise:

- A Screening Period of maximum 28 days.
- Five treatment periods during which subjects will be resident from the morning of Day -2 until at least 72 hours after dosing in Treatment Period 5; discharged on the morning of Day 4 of Treatment Period 5.
- A Follow-up Visit 7 to 14 days after the last dosing.

There will be a minimum washout period of 5 days between each dose administration.

A total of 25 healthy male and female subjects will be randomised into one of 5 treatment sequences to ensure at least 20 evaluable subjects at the end of the last treatment period. Each subject will receive 5 single-dose treatments of verinurad and allopurinol or verinurad alone:

- Treatment 1: verinurad prolonged release HPMC capsule 12mg and allopurinol tablet 300mg, as a free combination, fasted state.
- Treatment 2: verinurad/allopurinol FDC capsule 12/300 mg, fasted state.
- Treatment 3: verinurad/allopurinol FDC capsule 12/300 mg, fed state.
- Treatment 4: verinurad prolonged release HPMC capsule 12mg and allopurinol tablet 300mg, as a free combination, fed state.
- Treatment 5: verinurad prolonged release gelatin capsule 12 mg, fasted state.

All subjects will be instructed to drink approximately 2 L to 2.5 L of liquid a day, starting on Day -2 and throughout the stay at the clinic.

[figure not shown]
Subjects will follow an overnight fast of at least 10 hours before the dosing procedures: for the fed dosing, a high-fat, high-calorie breakfast (see Section 0) will be served 30 minutes before the planned administration of IMP, and is to be consumed in full at least 5 minutes before dosing; for the fasted dosing, no breakfast will be served. A meal can be given 4 hours after administration of IMP for both dosing states.

Details on IMP administration and food and fluid restrictions in relation to IMP administration are provided in Section 5.4.3.

The study flow-chart is presented in Figure 3-1. The SoA displaying assessments/tasks and time-points is presented in Table 3-1.

The study design is deemed appropriate for conduct in healthy volunteers during the COVID-19 pandemic (Section 3.3.3).

Figure 3-1 Study Flow Chart

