5.4. TREATMENTS

5.4.1. Identity of the Investigational Medicinal Product

Details on the identity of the IMP are presented in [Table 5-1](#).

Table 5-1 Identity of the Investigational Medicinal Product

Supplier:	AstraZeneca
Formulations:	Verinurad prolonged release HPMC capsule 12 mg Verinurad prolonged release gelatin capsule 12 mg Verinurad/allopurinol FDC capsule 12/300 mg Allopurinol tablet 300 mg
Strength/concentration:	Verinurad: 12 mg Allopurinol: 300 mg
Dose:	Verinurad: 12 mg Allopurinol: 300 mg
Route of administration:	Oral
Specific device for drug administration, if applicable:	Not applicable

Supplier:	AstraZeneca
Regimen:	Treatment 1: verinurad prolonged release HPMC capsule 12mg and allopurinol tablet 300mg, as a free combination, fasted state Treatment 2: verinurad/allopurinol FDC capsule 12/300 mg, fasted state Treatment 3: verinurad/allopurinol FDC capsule 12/300 mg, fed state Treatment 4: verinurad prolonged release HPMC capsule 12mg and allopurinol tablet 300mg, as a free combination, fed state Treatment 5: verinurad prolonged release gelatin capsule 12 mg, fasted state

Details of the batch numbers will be included in the Trial Master File and the final CSR.

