5.8. Premature Termination of the Study

The study must be terminated prematurely if:

- The PI and the Sponsor assess that the number and/or severity of AEs justify discontinuation of the study.
For instance, when there is 1 case of SAE considered at least possibly related to the IMP by the PI and the Sponsor.
The Sponsor considers the applied doses of the study drug to be no longer relevant.
- The Sponsor decides to discontinue the study.
- Data, that were not known before, become available and raise concern about the safety of IMP so that continuation would pose potential risks to the subjects.

- New data become available regarding COVID-19, which raises concern for the safe study conduct so that continuation would pose potential risks to the subjects or the study site staff.

Premature termination of the study must be mutually agreed upon by the PI and the Sponsor and must be documented. However, study results will be reported according to the requirements outlined in this CSP as far as applicable.

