6.3.1.4. Recording of Adverse Events

Time Period for Collection of Adverse Events

Adverse events will be collected from the first administration of the IMP throughout the treatment periods up to and including the Follow-up Visit.

Serious adverse events will be recorded from the time of informed consent.

Follow-up of Unresolved Adverse Events

Any AEs that are unresolved at the subject's last visit in the study are followed up by the Investigator for as long as medically indicated, but without further recording in ClinBase™.

AstraZeneca retains the right to request additional information for any subject with ongoing AE(s)/SAE(s) at the end of the study, if judged necessary.

Variables

The following variables will be collected for each AE:

- AE diagnosis/description
- The date and time when the AE started and stopped
- Intensity
- Whether the AE is serious or not
- Investigator causality rating against the investigational product (yes or no)
- Outcome

In addition, the following variables will be collected for SAEs:

- Date AE met criteria for serious AE
- Date Investigator became aware of serious AE
- AE is serious due to
- Date of hospitalisation
- Date of discharge
- Probable cause of death
- Date of death
- Autopsy performed
- Causality assessment in relation to Study procedure(s)
- Causality assessment to other medication

The following intensity ratings will be used:

- 1 Mild (awareness of sign or symptom, but easily tolerated)
- 2 Moderate (discomfort sufficient to cause interference with normal activities)
- 3 Severe (incapacitating, with inability to perform normal activities)

It is important to distinguish between serious and severe AEs:

- Severity is a measure of intensity whereas seriousness is defined by the criteria in [Appendix A](#).
- An AE of severe intensity need not necessarily be considered serious. For example, nausea that persists for several hours may be considered severe nausea, but not a SAE. On the other hand, a stroke that results in only a limited degree of disability may be considered a mild stroke but would be an SAE.

Causality Collection

The Investigator will assess causal relationship between investigational product and each AE, and answer “yes” or “no” to the question “Do you consider that there is a reasonable possibility that the event may have been caused by the investigational product?”

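### The Section 5.7 withdrawal criterion for severe or serious events names verinurad only, so a severe, non-serious event attributed to allopurinol alone does not force withdrawal on relatedness

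*Protocol*

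**What the plan says.** Protocol Section 5.7 opens with a general rule: "Dosing for any individual subject must be stopped if the subject experiences a possibly IMP-related SAE or a possibly IMP-related significant non-serious AE". A clause on the Principal Investigator's opinion that discontinuation is warranted follows. A list of situations requiring discontinuation comes next, among them the subject's own decision and clinically relevant changes in safety variables that make further dosing unjustified.

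The study-specific criteria then begin with a rule that does not depend on the drug: "If the subject reports symptoms which are considered unacceptable by the subject or the PI, he/she must be withdrawn from the study". Under it stands the criterion at issue: "Any other severe or SAE that is judged as possibly related to verinurad by the Investigator".

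Elsewhere relatedness is judged against the whole product:

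- Section 5.8 gives as an example for stopping the study: "For instance, when there is 1 case of SAE considered at least possibly related to the IMP by the PI and the Sponsor".
- Section 6.3.1.4 collects, for each adverse event, one yes/no causality rating against the investigational product.
- Table 5-1 in Section 5.4.1 lists the allopurinol tablet and the fixed-dose combination capsule among the investigational products.

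Section 6.3.1.4 also separates severity from seriousness: "An AE of severe intensity need not necessarily be considered serious".

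**The concern.** The criterion is narrower than the rules around it, and nothing in the protocol explains why one of the two drugs is left out. An investigator who follows the text literally must withdraw a subject with a severe, non-serious reaction if verinurad may have contributed, but not if the reaction is put down to allopurinol alone.

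The omitted drug carries a named risk. Section 3.3 lists rash among the most common adverse events of allopurinol and names maculopapular exanthema as one form of its hypersensitivity reactions. Each subject is scheduled for four allopurinol doses, so a reaction after the first would be followed by up to three more. The subjects are healthy and have no direct benefit from taking part, so there is no evident reason for a mandatory stopping rule to be weaker for one component.

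The criterion also fits the collected data poorly. For a non-serious event the only causality item is the single rating for the investigational product. The additional causality items apply to serious events and concern other medication and study procedures. The listed variables therefore cannot show whether a verinurad-only criterion was met or followed.

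**Working it through.** The plan gives no figure to reproduce. The check compares the rules and counts cases.

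**Step 1: routes to stopping that rest on severity or seriousness plus relatedness alone.** Section 5.7 offers two: the opening rule, judged against the IMP, and the study-specific bullet, judged against verinurad. In the opening rule, the clause on the investigator's opinion is read as attached to the significant non-serious event and not to the serious one.

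| Event | Possibly related to verinurad | Attributed to allopurinol alone |
|---|---|---|
| Serious | Stop: opening rule and bullet | Stop: opening rule |
| Severe, non-serious | Withdraw: bullet | No trigger on relatedness |

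Three of the four cells lead to mandatory stopping and one does not. If the opinion clause also governs serious events, the serious, allopurinol-alone cell loses its automatic trigger too, and two of four remain. The count of three is the reading more favourable to the plan.

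**Step 2: other routes for the open cell.** Each needs something beyond severity and relatedness:

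- the opening rule needs the investigator to consider the event significant and to hold that it warrants discontinuation;
- the safety-variable rule needs a view that further dosing is unjustified;
- the symptom rule needs the subject or the investigator to find the symptoms unacceptable;
- the subject may decide to stop.

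**Step 3: events that attribution does not affect.** Creatinine elevation and symptoms of acute uric acid nephropathy (Section 5.7 and Appendix D), a confirmed urinary calculus (Appendix D) and potential Hy's Law cases (Section 5.7 and Appendix C) have their own rules. The open cell is therefore confined to other severe, non-serious events, such as a severe rash that meets no seriousness criterion.

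**Step 4: exposure.** Inputs are 25 randomised subjects and five treatments (Section 3.1). Allopurinol is in Treatments 1 to 4 and verinurad is in all five. If every subject completes:

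- all doses: 25 × 5 = 125;
- doses containing allopurinol: 25 × 4 = 100;
- doses containing verinurad: 25 × 5 = 125, which includes all 100 allopurinol doses;
- allopurinol doses still scheduled for a subject after the first: 4 − 1 = 3.

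No allopurinol dose is given without verinurad. To reach the open cell, the investigator must rule out even a possible contribution from verinurad taken at the same time.

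**The case against.** The strongest reply is that the subject is already protected by rules that do not depend on the drug. The opening rule reaches an allopurinol-related severe event once the investigator thinks it warrants stopping. The safety-variable rule includes adverse events, and the symptom rule applies whatever the cause. The challenged bullet adds to these rules and does not narrow them.

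Severe intensity is defined in Section 6.3.1.4 as incapacitating. The gap therefore needs an investigator who sees an incapacitating reaction to allopurinol in a healthy volunteer, finds none of these rules met, and re-doses a subject who does not object. Other safeguards reduce the chance further:

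- If the reaction needs medication, Section 5.5 requires a decision on continuation after consulting the sponsor's lead physician.
- Adverse event questioning and a brief physical examination, which covers the skin, take place on Day -1 of Periods 2 to 5.
- Carriers of HLA-B*58:01 and subjects with known hypersensitivity are excluded.
- The gravest allopurinol reactions would ordinarily be serious and so fall under the opening rule.

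It can also be said that the three-of-four count is an unweighted count of logical cells, that 100 of 125 doses measures exposure and not risk, and that Section 5.8 concerns serious events, which lie outside the gap.

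Most of this stands as to size. The count is not a probability, Section 5.8 matters only as evidence of how the protocol judges relatedness, and attribution to allopurinol alone should be rare. The reply does not remove the inconsistency. Each alternative route needs a further judgement or choice, whereas the bullet makes withdrawal mandatory without one for verinurad. The single causality rating makes an attribution to allopurinol alone unlikely to be recorded, but it equally means that the record cannot support a verinurad-only rule.

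**Conclusion.** The concern holds. The withdrawal criterion in Section 5.7 is tied to verinurad while the surrounding rules and the causality data refer to the IMP. One of four combinations, severe and non-serious with attribution to allopurinol alone, has no mandatory withdrawal on relatedness. This rests on reading the investigator-opinion clause as applying only to non-serious events; on the other reading the gap is wider.

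The impact is low. The documents give no event rate, the number of such events is likely to be very small, and affected subjects are not unprotected. Sample size and pharmacokinetic analysis do not change. The point should still be corrected, because the wording is an operative stopping rule in healthy volunteers. Confidence is high for the mismatch in the text; no claim is made that harm is likely.

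**What to change.** In the Section 5.7 bullet, replace verinurad with IMP (verinurad and/or allopurinol). The criterion would then require withdrawal for any other severe adverse event, or any other serious adverse event, that the investigator judges possibly related to either component. This matches the opening rule of Section 5.7, Section 5.8 and the causality rating in Section 6.3.1.4, and it lets adherence be checked from the causality data already collected.

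The cost is one wording change in one bullet.

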Treatment 1: verinurad prolonged release HPMC capsule 12mg and allopurinol tablet 300mg, as a free combination, fasted state.

Treatment 2: verinurad/allopurinol FDC capsule 12/300 mg, fasted state.

Treatment 3: verinurad/allopurinol FDC capsule 12/300 mg, fed state.

Treatment 4: verinurad prolonged release HPMC capsule 12mg and allopurinol tablet 300mg, as a free combination, fed state.

Treatment 5: verinurad prolonged release gelatin capsule 12 mg, fasted state.

IMP: Investigational Medicinal Product.

Table 3-1 Schedule of Assessments

	Screening	Admission	Treatment Periods 1, 2, 3, 4, and 5		Follow-up Visit	Corresponding Section in Protocol
Visit	1	2		3		
Study Day	Day -28 to -3	Day -2	Day -1	Day 1 to 4	7 to 14 days post final dose	
Inclusion/exclusion criteria	X	X	X ^a			Sections 4.1.1 and 4.1.2
Demographic data	X					Section 11.2.3.1
Medical history	X					Section 11.2.3.1
Urinary drug/alcohol/cotinine screen	X	X				Section 6.3.2.8
Serology	X					Section 6.3.2.6
Informed consent	X					Section 8.5
HLA-B*58:01 allele genotyping	X					Section 6.3.2.3
Randomisation			X ^b			Section 5.1.1
Study Residency:						
Check-in		X (in the morning) ^c				Section 3.1
Check-out				Day 4 (after 72 h post-dose assessments) ^c		Section 3.1
Non-residential visit	X				X	Section 3.1
Verinurad and Allopurinol (verinurad only for Treatment 5) Administration:				Day 1 (0 h)		Sections 3.1 and 5.4.3

	Screening	Admission	Treatment Periods 1, 2, 3, 4, and 5		Follow-up Visit	Corresponding Section in Protocol
Visit	1	2		3		
Study Day	Day -28 to -3	Day -2	Day -1	Day 1 to 4	7 to 14 days post final dose	
Safety and Tolerability:						
Tympanic temperature ^d	X	X	X ^e	X	X	Section 6.3.5
Adverse event questioning and reporting ^f	X	X	X ^e	Spontaneous plus Day 1: pre-dose, 3 and 12 h post-dose Day 2: 24 h post-dose Day 3: 48 h post-dose Day 4: 72 h post-dose	X	Section 6.3.1
Prior and concomitant medications questioning	X	X	X ^e	X	X	Section 11.2.4.1
Blood pressure and pulse (supine)	X	X	X ^e	Day 1: Pre-dose Day 4: 72 h post-dose	X	Section 6.3.5
Safety 12-lead electrocardiograms	X				X	Section 6.3.4
Clinical laboratory evaluations ^g	X	X	X ^e		X	Section 6.3.2
Physical examination	X	X (brief)	X (brief) ^e	Day 4: 72 h post-dose (brief)	X	Section 6.3.3
Body weight and height, BMI	X					
Pregnancy test ^h	X	X			X	Section 6.3.2.5
COVID-19 Assessments						
Pre-visit phone call ⁱ	X	X			X	
SARS-CoV-2 RT-PCR		X ^j				Section 6.3.2.7
SARS-CoV-2 antibody	X					Section 6.3.2.7

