10.1.2. Laboratory Assessments

Haematology and clinical chemistry values will be listed by subject and time point including changes from baseline and repeat/unscheduled measurements. Summary tabulations including absolute values and changes from baseline will be presented by time point for the safety analysis set. The baseline for the measurements in Treatment Period 1 will be the Day -2 assessment and for the measurements in Treatment Period 2, 3, 4, and 5, it will be the Day -1 assessment performed prior to dosing in each of the respective treatment periods. Shift tables will also be presented.

Any laboratory variables with results from the laboratory given as “< xx” or “>xx” in the database will be imputed with the absolute value of the number without the sign (eg, < 2.2 will be imputed as 2.2) for the descriptive statistics and changes from baseline.

The listings will include the following information: test name, date of measurement, reference range, result and flags for any measurements that are outside the reference range (eg, AstraZeneca, program, or laboratory ranges). Clinical laboratory data will be reported in System International units in the CSR.

Additional listings will be presented for the following:

- Urinalysis (macroscopic and microscopic, if applicable)
- Pregnancy testing (including FSH)
- The results of viral serology, SARS-CoV-2 virology, and the drugs of abuse, alcohol, and cotinine screen will not be listed in the CSR.

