
Appendix D Actions Required in Cases of a Renal-related or Urolithiasis Treatment-emergent Adverse Event or a Serum Creatinine Elevation

During the course of the study, the Investigator will remain vigilant for symptoms or signs of renal-related events, kidney stone events or changes in renal function.

D 1 Signs and Symptoms Suggestive of Urolithiasis

After initiation of study medication, if a subject experiences signs or symptoms suggestive of nephrolithiasis (eg, flank pain or haematuria), he/she should be evaluated by a physician and serum creatinine, blood urea nitrogen, and urinalysis should be measured via central laboratory testing (preferred) and/or local laboratory testing, as appropriate, to determine renal function. Imaging (intravenous urogram, renal ultrasound, or magnetic resonance imaging) is recommended to confirm or exclude any urinary tract calculus. Abnormal results should be treated as medically appropriate by the treating physician. All symptoms, testing, and results will be documented in source documents and ClinBase™.

If a subject develops a urinary tract calculus (as confirmed and documented by imaging or passage of a stone) at any time during the study, the subject will discontinue randomised study medication and be encouraged to remain in the study for continued safety assessments. If the urinary tract calculus is passed, it should be collected and submitted to pathology for analysis of chemical composition.

D 2 Deterioration of Renal Function

The Investigator should assess subjects exhibiting elevated serum creatinine carefully to determine the most likely cause for the deterioration of renal function. Following a thorough assessment, the subject should be managed according to local medical practice. Potentially-treatable causes such as volume depletion, hypotension etc., should be corrected before following the recommendations given below.

Serum Creatinine Increase to ≥ 1.5 -fold from Baseline

- Assess the subject to identify and manage any potential contributing factor. Correct any dehydration and ensure the subject is well hydrated prior any future evaluation.
- Contact the Sponsor's lead physician for advice and to discuss discontinuation of study medication.

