- Assess creatinine daily if the elevation is detected while the subject is admitted to the Clinical Unit, and otherwise weekly.
- Subsequent management will depend on the repeat measurement(s):
 - If serum creatinine < 1.5 -fold of baseline value for 2 successive measurements, the subject may restart/continue with study treatment on the original study visit schedule.

- If repeat serum creatinine is ≥ 1.5 -fold of baseline, the subject should be evaluated every week until normalisation. The randomised treatment should be permanently discontinued.

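### For a 1.5-fold creatinine rise, Section 5.7 requires treatment to stop while Appendix D 2 leaves the dosing action open, and the scheduled in-house check comes the day before a dose

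*Protocol*

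**What the plan says.** Section 5.7, in its list of situations in which subjects must come off investigational product, says: "Study treatment must be stopped if a subject has elevated serum creatinine levels greater than 1.5 times the pre-treatment value". It adds that a "retest of the creatinine should be performed as soon as possible" and points to Appendix D, which it describes as containing criteria for stopping.

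Appendix D, D 2, covers a creatinine increase to at least 1.5-fold from baseline. After assessment and hydration, the investigator is to contact the sponsor's "lead physician for advice and to discuss discontinuation of study medication". On retesting it says: "Assess creatinine daily if the elevation is detected while the subject is admitted to the Clinical Unit" (weekly otherwise). If creatinine is below "1.5 -fold of baseline value for 2 successive measurements, the subject may restart/continue with study treatment on the original study visit schedule". If the repeat is still at least 1.5-fold: "The randomised treatment should be permanently discontinued".

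In Table 3-1 the row "Clinical laboratory evaluations" is marked at Screening, Day -2, Day -1 (footnote e: Periods 2 to 5 only) and Follow-up, with nothing on Days 1 to 4. Section 10.1.2 defines a laboratory baseline for listings and summaries: Day -2 for Period 1, while "for the measurements in Treatment Period 2, 3, 4, and 5, it will be the Day -1 assessment performed prior to dosing".

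**The concern.** Two sections of one protocol deal with the same laboratory event in different terms. Section 5.7 acts on a single value and stops treatment. D 2 acts on a single value by opening a discussion, and its only mandatory stop comes with the repeat value. The trigger also differs (above 1.5 against at or above 1.5), as does the reference (pre-treatment value against baseline).

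Section 3.3 names creatinine elevation above 1.5 times baseline as the main toxicity concern with verinurad alone in healthy subjects. It relies on co-administered allopurinol as mitigation, except in Treatment 5. In four of the five sequences (all but 12345) Treatment 5 is followed by another dose. An investigator holding a raised value the day before dosing has to know whether the next dose is withheld, in volunteers who have no direct benefit from the study.

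**Working it through.** **1. When creatinine is measured.** Counting from Table 3-1: Screening 1 + Day -2 of Period 1 1 + Day -1 of Periods 2 to 5 4 + Follow-up 1 = 7 samples. At 7.5 mL each this is 52.5 mL, which reproduces the clinical chemistry line of Table 7-1 (7 samples, 52.5 mL). Five of the seven come after a dose. Four of those five are on Day -1 of the next period. The fifth is Follow-up, when no dose remains.

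**2. How close the check is to the next dose.** Dosing is on Day 1 (Section 5.4.3). Subjects stay in the unit from Day -2 until Day 4 of Period 5, so D 2's daily branch applies. Take the Day -1 sample at about -24 h relative to the next dose:

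- First daily retest: -24 + 24 = 0 h (Day 1).
- Second daily retest: -24 + 48 = +24 h (Day 2).

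At a strictly daily frequency one clearing value is available when the Day 1 dose is due, and the second follows about 24 h later. An extra retest on Day -1 plus a pre-dose value on Day 1 would give two values in time.

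**3. The two instructions side by side.**

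| | Section 5.7 | Appendix D 2 |
|---|---|---|
| Trigger | above 1.5 times | at least 1.5-fold |
| Reference | pre-treatment value | baseline, not named |
| Dosing at first raised value | must stop | discuss discontinuation; no hold ordered |
| Retest | as soon as possible | daily while resident |
| Resumption | left to Appendix D | restart or continue, original schedule, after two values below 1.5-fold |
| Permanent stop | not stated for creatinine | repeat value at least 1.5-fold |

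The word *restart* presupposes a stop. *Continue*, and an instruction only to discuss discontinuation, do not.

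**4. How often.** Section 3.3 gives 1.7% of healthy subjects on verinurad monotherapy. Applied per subject: 25 x 0.017 = 0.425 subjects expected, and 1 - 0.983^25 = 0.349 as the chance of at least one. I use these only as upper figures. Four of the five treatments include allopurinol, hydration is mandated, and Section 3.3 describes the elevations as mostly transient. With the minimum 5-day washout, the Day -1 check comes at least 5 - 1 = 4 days after the previous dose.

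**The case against.** The best defence is that the two sections are successive steps of one procedure. Section 5.7 imposes a stop and a retest. D 2 then says when the subject may restart and when the stop becomes permanent. The next bullet of Section 5.7, on suspected acute uric acid nephropathy, says permanent where it means permanent, so the creatinine bullet can be read as a hold. D 2 calls its content recommendations, which would not displace a mandatory stop in the body, and nowhere tells the investigator to dose a subject with a raised value. Section 5.7 also has a general provision for clinically relevant laboratory changes. This is probably what was meant, and it lowers the risk of harm. It does not explain *continue* or the discussion wording, and D 2 still does not say what happens to a dose that falls due before the two values are in hand.

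Two stronger readings are tempting and are not supported:

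- A reader might infer that two clearing retests can never precede the Day 1 dose. Section 5.7 asks for a retest as soon as possible and subjects are resident, so a same-day retest plus a pre-dose value is feasible. Daily testing in D 2 need not be a maximum.
- A reader might infer from Section 10.1.2 that the stopping reference resets each period, so that stepwise rises accumulate unseen. That baseline is written for listings and summaries, and nothing applies it to stopping decisions. Section 5.7's pre-treatment value is most naturally the value before any study drug. What remains is that D 2 should name its reference.

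**Conclusion.** The point holds as an inconsistency in a safety stopping rule. Section 5.7 requires a stop. D 2, to which it refers, orders no hold at the first raised value and uses wording that allows dosing to continue. The trigger differs only at exactly 1.5-fold, and D 2's baseline is not identified.

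The inconsistency has practical weight because all four scheduled in-house post-dose checks fall the day before a dose, and at daily retesting the second clearing value comes about 24 h after that dose is due unless an extra retest is done. This assumes a Day -1 sample about 24 h before dosing and no unscheduled creatinine earlier in the period. The expected number affected is at most about 0.4 of 25, taking the monotherapy rate as an upper figure. No estimate, interval or sample-size statement changes. It should be fixed because the conflict concerns the protocol's main toxicity signal and the correction costs almost nothing.

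**What to change.** Put one rule in both Section 5.7 and D 2:

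- **Reference:** the pre-first-dose creatinine (Day -2, Period 1), stated to govern stopping decisions whatever baseline Section 10.1.2 uses for summaries.
- **Trigger:** at least 1.5 times that value.
- **Action:** withhold further dosing, retest as soon as possible and at least daily while resident, and contact the sponsor's lead physician.
- **Resumption:** only after two successive values below 1.5-fold. If they are not available when a dose falls due, delay the dose (the 5-day washout is a minimum) or omit it. A subject who clears in time is dosed as planned.
- **Permanent discontinuation:** if the repeat is at least 1.5-fold.

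In D 2 this replaces the instruction to discuss discontinuation, the word *continue* and the reference to the original visit schedule.

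The cost is protocol wording. D 2 already calls for the retests. Two at 7.5 mL take the Table 7-1 total from 447.7 to 447.7 + 15.0 = 462.7 mL, within the 500 mL limit. The downside is a rare delayed or omitted period for an affected subject, against 5 subjects randomised beyond the 20 evaluable needed.
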